6.1 Variables

The following pharmacokinetic parameters will be determined using the actual recorded sampling times and non-compartmental method(s) with Phoenix WinNonlin (Version 6.2 or higher): C_{max} (only for CFZ533 cohort) - The highest concentration observed during a dosing interval and C_{trough_ss} - The trough observed analyte concentration at the end of a dosing interval.

6.2 Descriptive analyses

Plasma CFZ533 and serum VAY736 concentration will be summarized by treatment, and visit/sampling time point. Descriptive summary statistics will be provided, including the frequency (n, %) of concentrations below the LLOQ and reported as zero.

Summary statistics will include mean (arithmetic and geometric), SD, CV (arithmetic and geometric), median, minimum and maximum. Concentrations below LLOQ will be treated as zero in summary statistics and for PK parameter derivation. Zero values will be treated as missing data when calculating geometric mean and geometric CV.

Pharmacokinetic parameters will be summarized by treatment with descriptive statistics as above. Graphical methods will be employed to show mean and individual concentration-time profiles over the whole study by treatment, with time defined as visit and actual day respectively.

7 Statistical methods for Pharmacodynamic (PD) parameters

All patients within the PD analysis set will be included in the PD data analysis.

7.1 Primary objective

The primary objective is to determine the effect of VAY736 and of CFZ533 versus their respective placebo on disease activity in SLE patients at Week 29 compared to baseline. The primary analysis will compare active treatment with its matching placebo based on the PD analysis set within either cohort independently.

7.1.1 Variables

The primary endpoint is a composite of SRI-4 response at Week 29 with sustained reduction in oral corticosteroid from Week 17 through Week 29.

SRI-4 response is defined as below:

- having ≥ 4 points reduction from baseline in SLEDAI-2K score AND
- no new BILAG-2004 A organ domain score and no more than one new BILAG-2004 B organ domain scores compared with baseline AND
- < 0.3 mm or < 10 mm point increase if scaled 0 to 3 or 0 to 100 mm, respectively in the physician's global assessment from baseline

Sustained reduction in oral corticosteroids is defined as below:

- ≤ 5 mg/day or \leq baseline dose, whichever is lower, at Week 17
AND
- no increase of that dose from Week 17 through Week 29

When all these criteria are met, the patient is considered as a responder. However, patients receiving CS dosing in addition to the baseline CS dosing levels or subsequent, reduced levels attained at Week 17 after completing the guided corticosteroid tapering period will be considered non-responder for primary endpoint:

- if total daily CS dose is > 30 mg/d prednisone or equivalent, or
- increased daily CS dose is administered > 2 days within a 4-week treatment cycle, or
- daily CS dose is increased within 2 weeks of Study Visit Week 29.

Patients who have taken other rescue medication or prohibited medication (Table 6-3 of study protocol, e.g., new immune suppressive agents or biologics) or drop out before Week 29 will also be considered non-responder for the primary endpoint. Where acute CS administration occurs for purposes other than the treatment of SLE disease activity, patient responder status will be discussed on a case-by-case basis.

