6.1.3 Treatment arms/group

6.2 Other treatment(s)

6.2.1 Concomitant therapy

Permitted standard-of-care co-medications include oral CS and/or an anti-malarial agent (e.g., hydroxychloroquine) and/or thalidomide and/or one of the listed DMARDs: (see Inclusion criteria [Section 5.1](#)).

Table 6-2 Allowed concomitant medications

Medication	Condition
Ad hoc use of oral analgesics (NSAIDs, acetylsalicylic acid, paracetamol)	All use must be recorded in the concomitant medications / significant non-drug therapies
Corticosteroids	If CS is patient's single, SoC medication, an oral dose ≤ 30 mg/d ≥ 8 weeks prior randomization and stable dose for ≥ 2 weeks prior to randomization If CS is not patient's single SoC medication, an oral, stable dose of ≤ 30 mg/d for ≥ 2 weeks prior to randomization

CCI	
	Maintain baseline CS dosing from Study Week 1 to Week 5
Anti-malarials	Anti-malarial drugs (i.e., hydroxychloroquine, chloroquine, quinacrine) and/or thalidomide at stable dosing ≥ 8 weeks prior screening and remaining stable throughout blinded treatment period. Substitution between anti-malarial drugs is permitted if equivalent dosing is maintained.
DMARDs	Methotrexate or an imidazole derivative (e.g., azathioprine, mizoribine) or a mycophenolic acid derivative (e.g., mycophenolate mofetil) if at stable dosing ≥ 8 weeks prior to randomization and remaining stable throughout blinded treatment period.

Medication	Condition
	Any DMARDs that will be discontinued by the patient prior to study entry will require a minimum wash-out period of 4 weeks (methotrexate requires 8 weeks) or 5 half-lives, whichever is longer, unless noted otherwise in the protocol

Each concomitant drug must be individually assessed against all exclusion criteria/prohibited medication. If in doubt, the investigator should contact the Novartis medical monitor before randomizing a subject or allowing a new medication to be started. If the subject is already enrolled, contact Novartis/sponsor to determine if the subject should continue participation in the study.

All medications, procedures and significant non-drug therapies (including physical therapy and blood transfusions) administered after the subject was enrolled into the study must be recorded in the concomitant medications / significant non-drug therapies

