6.2.3 Prohibited medication

Use of the treatments displayed in the below [Table 6-3](#) are not allowed after the start of the study.

Table 6-3 Prohibited medication

Medication	Prohibition period	Action taken
Other immune suppressive agents and biologics: 
 • Calcineurin inhibitors • Cyclophosphamide, intravenous Ig, plasmapheresis, anti-TNF-α mAb, CTLA4-Fc Ig (abatacept) or BAFF targeting agents (e.g., belimumab) • Any B cell depleting therapies (e.g., anti-CD20 mAb, anti-CD22 mAb, anti-CD52 mAb), atacicept, (TACI-Ig) 	Throughout treatment period through EoS	Withdrawal may be required on a case-by-case basis
• Total CS >30 mg/d prednisone or equivalent	Throughout treatment period through Week 29	Designated non-responder for primary endpoint
• Changes in CS dose	Within 2 weeks of Study Visit Week 29	Designated non-responder for primary endpoint
• Other experimental therapies	Throughout treatment period through to EoS	Withdrawal may be required on a case-by-case basis
• Live/ attenuated vaccines	
 • For Cohort 1 (VAY736): Throughout treatment period and follow up period up to 2 years after the EoT or until achieving B cell recovery (whichever occurs earlier) • For Cohort 2 (CFZ533): Throughout treatment period and up to 14 weeks after last CFZ533 dosing 	Study treatment discontinuation; patient should remain in study and follow visit schedule for safety monitoring until achieving EoS visit for their respective cohorts

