6.2.4 Rescue medication

Corticosteroids may be administered to patients for SLE clinical disease flares after enrollment into this study as determined necessary by the responsible PI. However, patients receiving increased CS dose will be considered non-responders for primary study endpoint if any of following criteria was met:

- total daily CS dose is >30 mg/d prednisone or equivalent, or
- increased daily CS dose is administered >2 days within a 4-week treatment cycle from Week 17 to Week 29, or
- daily CS dose is increased within 2 weeks of Study Visit Week 29.

Where acute corticosteroid administration occurs for purposes other than the treatment of SLE disease activity, such as short-acting hydrocortisone dosed peri-operatively in patients with suppressed hypothalamic-pituitary-adrenal axis, patient responder status will be discussed on a case-by-case basis.

All Concomitant Medications as well as their dose changes must be recorded in the eCRF.

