Tuberculosis test ⁷	X																		X	
Pregnancy test ⁵	X	X		X	X	X	X	X	X	X	X	X	X	X	X	X	X		X	
Hematology ⁷	X	X		X	X	X	X	X	X	X	X	X	X	X	X	X	X		X	
Clinical Chemistry ⁷	X	X		X	X	X	X	X	X	X	X	X	X	X	X	X	X		X	
CCI																				
Coagulation Panel ⁷	X	X ⁶					X ⁶				X ⁶								X ⁶	
Autoantibodies ⁷	X	X					X				X				X				X	
CCI																				
IMI blood sample ^{7, 16}		X			X					X										
IMI urine sample ^{7, 16}		X			X					X										
CCI																				
Steroid taper ¹¹					X	X	X	X												
PK Cohort 1 ¹²			X	X	X	X	X	X	X	X	X	X	X	X	X	X	X	X	X	
PK Cohort 2 ¹²			X ¹³	X	X ¹³	X	X ¹³	X	X	X	X ¹³	X	X ¹³	X	X ¹³	X	X ¹³		X	
Immunogenicity ^{12, 14}		X		X			X				X	X			X				X	
CCI																				

Epoch	Screening		Treatment																EoT
Visit Name	Screen	Base-line ²	Treatment – blinded period								Treatment – open label period								EoT
Visit Numbers ¹	1	20	110	120	130	140	150	160	170	180	190	200	210	220	230	240	250	260	299
Days	-28 ±2	-1 to 1	1	15 ±2	29 ±2	57 ±2	85 ±2	113 ±2	141 ±2	169 ±3	197 ±3	211 ±2	225 ±3	253 ±3	281 ±3	309 ±3	337 ±4	340 ±1	365 ±5
Weeks	-4	-1 to 1	1	3	5	9	13	17	21	25	29	31	33	37	41	45	49	49	53
Months	-1	-1 to 1	1	1	2	3	4	5	6	7	8	8	9	10	11	12	13	13	14

IRT	X	X ²³		X	X	X	X	X	X	X	X	X	X	X	X	X	X		X
Dose administration ²¹			X ²²	X ⁶	X	X	X	X	X	X	X ²²	X ⁶	X	X	X	X	X		

Adverse Events	As required																		
Concomitant Treatment	As required																		
Comments	As required																		

^X Assessment to be recorded in the clinical database, EoT – End of Treatment

¹ Visit structure given for internal programming purpose only

² Baseline visit may be combined with Visit 110 at Day 1

³ Body Weight, Height (screening only), Temperature, Blood Pressure, Pulse Rate

⁴ Only for Cohort 1 (VAY736); i.v. CS to be applied approximately 1 hour before first dose

⁵ Pregnancy test on Visit 1 (Screening) in serum, all other visits in urine, only females

CCI

⁷ Central Lab

CCI

¹¹ Corticosteroids should be tapered down to 5 mg/day or lower

¹² Samples are collected pre-dose unless otherwise stated

¹³ Cohort 2 (CFZ533): take one PK sample at pre-dose and another sample 90 min AFTER THE START of i.v. infusion

¹⁴ Cohort 1 (VAY736): serum Cohort 2 (CFZ533): plasma

CCI

¹⁶ Only selected sites

CCI

²¹ Dosing must be done after all assessments are completed, except for PK blood sampling in Cohort 2 (CFZ533) at visits V110, 130, 150, 190, 210, 230 and 250 where pre and post dose blood sampling is required

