12.4.1 Definition of primary endpoint(s)

The primary endpoint is a composite of SRI-4 response at Week 29 with sustained reduction in oral corticosteroid from Week 17 through Week 29.

SRI-4 response is defined as below:

- having ≥ 4 points reduction from baseline in SLEDAI-2K score AND
- no new BILAG-2004 A and no more than one new BILAG-2004 B domain scores AND
- no worsening, i.e., < 10 mm increase from baseline if scaled 0-100 mm or 0.3-point increase from baseline if scaled 0 to 3 in the Physician's Global Assessment

Sustained reduction in oral corticosteroid is defined as below:

- ≤ 5 mg/day or \leq baseline dose, whichever is lower, at Week 17

AND

- No increase of that dose from Week 17 through Week 29 according to all of the following conditions.
 - total daily CS dose remains ≤ 30 mg/d prednisone or equivalent
 - any increased daily CS dose administered is ≤ 2 days within a 4-week treatment cycle from Week 17 to Week 29
 - daily CS dose is not increased within 2 weeks of Week 29 study visit

When all these criteria are met, the patient is a responder. Patients who receive rescue medication (see [Section 6.2.4](#)) will be considered as non-responder.

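### The steroid part of the primary endpoint has no single definition: the protocol conflicts with itself, and the SAP drops two of its limits

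*SAP*

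**What the plan says.** **Protocol 12.4.1** combines SRI-4 at Week 29 with a sustained steroid reduction. The second part is worded "No increase of that dose from Week 17 through Week 29 according to all of the following conditions". The conditions are a total of at most 30 mg/d, at most 2 days of increased dose per 4-week cycle between Weeks 17 and 29, and no increase within two weeks of the Week 29 visit. The section then closes with a sentence on "Patients who receive rescue medication", citing Section 6.2.4 and classing them as non-responders.

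**Protocol 6.2.4** fails a patient only above 30 mg/d, for an increase near Week 29, or for an increase lasting more than 2 "days within a 4-week treatment cycle from Week 17 to Week 29, or" one of the other tests. Section 3 likewise fails only patients who go beyond the rescue allowances.

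**Protocol Table 6-3** lists "Changes in CS dose" within two weeks of the Week 29 visit as a reason for non-response. Section 6.2.2 asks for a stable dose from Week 17 to Week 29.

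**SAP 7.1.1** states "no increase of that dose from Week 17 through Week 29" without the protocol's qualifier. It then fails patients whose steroid dosing exceeds the baseline level, or the reduced level reached at Week 17, for more than 2 "days within a 4-week treatment cycle, or" on either of the other two tests. No week limits are given. It also makes use of medication prohibited by protocol Table 6-3 a non-response.

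**Protocol Table 6-2** allows background antimalarials and DMARDs only if "remaining stable throughout blinded treatment period".

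**The concern.** This is the primary endpoint, and responder status is derived from recorded steroid doses. If the lines disagree, whoever programs the derivation chooses between them.

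The timing matters. Protocol 6.4 and Table 6-4 allow the statistician, programmers and trial team to see individual treatment assignments at interim analyses, and both documents leave some steroid use to case-by-case discussion. An unresolved rule could therefore be settled by people who know the assignments.

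The arms are small. One patient is 1/30 = 3.3 percentage points of an arm's responder rate.

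**Working it through.** **1. Apply each line to the same patient.** Assume SRI-4 is met, the Week 17 steroid target is met and the total dose stays at or below 30 mg/d. R = responder, N = non-responder, – = line not engaged.

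| Patient | 6.2.4 and 12.4.1 conditions | 12.4.1 closing sentence, literal | Table 6-3 | SAP no-increase line | SAP more-than-2-days line | SAP via Table 6-3 |
|---|---|---|---|---|---|---|
| A: 3-day increase above baseline at about Week 8 | R | N | – | R | N | – |
| B: 1- or 2-day increase at Week 20 | R | N | – | N | R | – |
| C: dose reduction within two weeks of Week 29 | R | – | N | R | R | N |

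- A differs **between documents**: the SAP omits the window and refers to baseline dosing.
- B is a conflict **within the protocol**. The SAP has a parallel one: a flat no-increase test followed by a more-than-2-days test. The dropped qualifier is a second between-document difference.
- C is a conflict **within the protocol**. The SAP holds both answers because it imports Table 6-3.
- A fourth patient, whose existing DMARD or antimalarial dose is raised before Week 29, departs from Table 6-2 but meets no visible non-responder rule. The SAP's examples are new immune suppressive agents and biologics.

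**2. The plan's own figure.** Protocol 12.8.1 gives an 84% chance of meeting the criteria with 30 per arm at 17% versus 42%, and about 10% with no difference. The criteria are Prob(difference > 0) > 90% and Prob(difference > 15 points) > 50%. The prior parameters are not in the visible text, so I assumed independent Beta priors, (1,1), (0.5,0.5) and (1/3,1/3), without covariates. Exact enumeration of 30 versus 30 gives 81.2% and 6.0%. This does not reproduce 84%. The design calculation may have used another prior, and nothing below depends on the gap.

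**3. Decision boundary.** For every placebo count from 0 to 10, all three priors need 5 more active than placebo responders. Example with Beta(1,1) and 5 placebo responders:
- 10 active: Prob(> 0) = 0.927 and Prob(> 15 points) = 0.525, so both criteria are met.
- 9 active: 0.882 and 0.407, so neither is met.

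**4. How often the result lies at the boundary.** Let X be the responder counts, with X_active ~ Bin(30, p_a) and X_placebo ~ Bin(30, p_p).

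| True rates | P(net 4) | P(net 5) | Sum |
|---|---|---|---|
| 42% vs 17% | 0.068 | 0.088 | 0.156 |
| 32% vs 17% | 0.120 | 0.120 | 0.240 |

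One added placebo responder reverses only the net-5 cases (about 9% and 12%). One removed placebo responder reverses only the net-4 cases (about 7% and 12%). Either requires that such a patient exists.

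**5. Illustrations with assumed shares.** The documents give no rescue rates.
- A stricter reading that removes 5% to 30% of responders in both arms lowers the chance of success from 81.2% to between 78.4% and 59.7%.
- The same removal in placebo only, with no true difference, raises it from 6.0% to between 6.9% and 13.5%.
- A looser reading that lifts placebo from 17% to 21% or 23%, with active held at 42%, lowers it to about 70% or 63%.

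**The case against.** **The intent can be recovered.** The closing sentence of 12.4.1 cites 6.2.4, which contains the allowances. Sections 3, 4.1 and 6.2.2 all speak of limited rescue. The SAP's more-than-2-days test would have no purpose after Week 17 if any increase failed. This is a fair reading of intent and probably how B would be programmed. It does not settle A or C, and the literal text still supports both answers for B.

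**Patient A is narrow.** The patient must exceed baseline before Week 17 and still meet the target and SRI-4. The SAP's mention of the completed taper could also be read as confining the rule to the later period. That is possible, but the bullet states no window and the sentence also names baseline levels.

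**Stronger readings the documents do not support:**
- *That every difference is protocol against SAP.* Only the missing window and the missing qualifier are. The other two conflicts start inside the protocol.
- *That a late dose reduction clearly passes the SAP.* It does not, because Table 6-3 is imported.
- *That the Week 29 pre-medication makes all of Cohort 1 non-responders.* Table 8-1, footnote 4, reads "Only for Cohort 1 (VAY736); i.v. CS to be applied approximately 1 hour before first dose". The composite concerns oral steroid, open-label dosing follows the Week 29 assessments, and steroid given for reasons other than SLE activity goes to case-by-case review.
- *That the ambiguity biases the difference towards zero.* The direction depends on which reading is used and which arm escalates more.

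**Redaction and setting.** Protocol 8.3.2 is blacked out, SAP 7.1.3.1 shows no text, and SAP 1.1 places derived-variable specifications in another document. A derivation or sensitivity analysis may exist there. The study is non-confirmatory and the criteria are a guide. These points limit the consequence, but the visible definitions still disagree.

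**Conclusion.** The point holds. Followed literally, the visible text gives at least three kinds of patient opposite responder status on the primary endpoint and leaves a fourth, the background-drug increase, unaddressed.

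One reclassified patient can move the result across the decision boundary. The results that a single change in a given direction would reverse have a probability of about 7% to 12% at the true rates examined. This rests on 30 per arm, assumed Beta priors and no covariate adjustment, and it is conditional on such a patient occurring. It measures how fragile the decision is. It does not estimate bias, whose size and sign cannot be known from the documents.

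**What to change.** Reconcile Protocol Sections 3, 6.2.2, 6.2.4, Table 6-3 and 12.4.1 and SAP 7.1.1 into one non-responder derivation:

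- Use the same dose, duration and time-window tests wherever the rule appears, and state whether a change or only an increase counts near Week 29.
- State what the 12.4.1 closing sentence means relative to the allowances.
- State how an increase of an existing background DMARD or antimalarial is handled.
- Fix the derivation without reference to treatment assignment, and date it.
- Report the main alternative reading as a sensitivity analysis.

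SAP Section 5 says that final Cohort 2 results were reported in an earlier interim report. For that cohort, document the derivation that was used and report the alternative beside it.

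Which clinical rule applies is for the sponsor. The cost is wording changes, one derivation table and one additional run. Concomitant medications and their dose changes are already recorded in the eCRF.

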Within the treatment cohort, blinded treatment with the investigational drug (VAY736 or CFZ533) or placebo will be administered on top of patients' stable standard of care therapy for SLE. Visits to assess safety and/or efficacy are scheduled at 4-week intervals. An additional safety visit is scheduled at Week 3 (within the placebo-controlled period) and Week 31 (within the open label period) where patients in Cohort 2 (CFZ533) will receive an additional treatment dose (see [Section 4.2.2](#)).

At the baseline visit Day 1, following patient eligibility confirmation and completion of all assessments, first dose of study drug/placebo will be administered. The last treatment in the blinded treatment period will be given at the Week 25 visit. The readout for the blinded treatment period will be performed at Week 29. Study drug will be administered every 4 weeks. Unless otherwise stated, all assessments must be completed BEFORE the next dose of study drug is administered.

Guided corticosteroid (CS) reduction

- Patients entering the study on a stable CS regimen are required to undergo a guided CS taper from baseline levels starting at Week 5 in order to achieve by Week 17:
 - a daily CS dose of ≤ 5 mg/day prednisone or equivalent,
 - or a CS dose that is less than the baseline dose, whichever is the lower dose.
- In addition, the patient should remain at the lowered CS dose achieved at Week 17 through to Week 29.
- Patients entering the study without background CS therapy should remain free of any CS regimen or increase in SoC DMARDs through to Week 29.
- Patients exceeding the rescue therapy allowances may continue in trial but will be labeled a non-responder for primary endpoint.
- During the open label phase, further reductions in patients' SoC CS and DMARDs may be made on an individual basis as deemed appropriate by the investigator. For details on the guided CS tapering please refer to [Section 6.2.2](#)

Open-label treatment phase

At the end of the Week 29 visit, after all assessments have been performed, the first -open label treatment will be administered. Patients in Cohort 1 will receive VAY736 and patients in Cohort 2 will receive CFZ533. Study drug will be administered every 4 weeks. The last treatment will be given at the Week 49 visit, and the End-of-Treatment (EoT) visit will be performed 4 weeks thereafter, at Week 53.

Follow-Up period

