4.1.1 Rationale for choice of SoC therapy

The antimalarial agent hydroxychloroquine has been used since the 1960s for controlling milder SLE disease manifestations (reviewed in Kaul et al 2016). More severe disease manifestations often require systemic CS therapy and cytotoxic therapies leading to numerous adverse effects common with chronic exposure to this drug class. Disease modifying anti-rheumatic drugs (DMARDs) such as methotrexate or an imidazol derivative (e.g., azathioprine, mizoribine) or mycophenolic acid derivatives (e.g., mycophenolate mofetil) are typically added as steroid-sparing agents to allow reduction of daily CS dosage. Thalidomide has emerged as second line treatment for severe, refractory mucocutaneous disease (Chasset et al 2018). Background therapy with CS and DMARDs in this trial will be limited to prevent potential over-immune suppression in patients receiving VAY736 or CFZ533. In addition, this study in SLE patients limits the severity of active kidney involvement, thus reducing potential for requiring higher corticosteroid dosing or addition of other cytotoxic drugs such as cyclophosphamide.

[figure not shown]
To reduce the high placebo responder rate typical of SLE trials, patients will be assessed for primary outcomes only after a defined period at a lowered CS dose achieved by a guided taper (Merrill et al 2017, Thanou and Merrill 2018).

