5.2 Exclusion criteria

Subjects meeting any of the following criteria are not eligible for inclusion in this study.

1. **Cohort 2 (CFZ533/Placebo) only:** Patients who are at significant risk for thromboembolic events based on the following:
 - History of either thrombosis or 3 or more spontaneous abortions
 - Presence of lupus anticoagulant or significantly prolonged activated partial thromboplastin time (aPTT) consistent with co-existent anti-phospholipid syndrome and without concurrent prophylactic treatment with aspirin or anticoagulants as per local standard of care
2. History of receiving prior to screening:
 - Within 12 weeks: high dose corticosteroids (i.e., ≥ 500 mg Solumedrol or equivalent), calcineurin inhibitors, or other oral DMARD except as listed in inclusion criterion 6
 - Within 24 weeks: cyclophosphamide or biologics such as intravenous Ig, plasmapheresis, anti-TNF- α mAb, CTLA4-Fc Ig (abatacept) or BAFF-targeting agents (e.g., belimumab)
 - Any B cell depleting therapies (e.g., anti-CD20 mAb, anti-CD22 mAb, anti-CD52 mAb) or TACI-Ig (atacept) administered within 52 weeks prior to screening, and a B cell count < 50 cells/ μ L at the time of screening.
3. Evidence of past exposure to tuberculosis (TB) as assessed by Quantiferon testing at screening. Patients with history of latent TB infection may be eligible if they have received and completed appropriate anti-TB treatment according to national guidelines
4. Presence of human immunodeficiency virus (HIV) infection at screening
5. Any of the following abnormal laboratory values:
 - Platelets $< 50,000/\text{mm}^3$ ($< 50 \times 10^9/\text{L}$)
 - Hemoglobin (Hgb) < 8.0 g/dL (< 5 mmol/L)
 - Neutrophil count ($< 1,000/\text{mm}^3$) ($< 1.0 \times 10^9/\text{L}$)
6. Have donated blood or experienced a loss of blood > 400 mL within 3 months prior study entry, or longer if required by local regulations
7. Severe organ dysfunction or life-threatening disease

8. Presence of severe lupus kidney disease as defined by proteinuria above 6 g/day or equivalent using spot urine protein creatinine ratio, or serum creatinine greater than 2.5 mg/dL (221.05 µmol/L), or requiring immune suppressive induction or maintenance treatment exceeding protocol defined limits
 9. Active viral, bacterial or other infections at the time of screening or enrollment, or history of recurrent clinically significant infection or of recurrent bacterial infections with encapsulated organisms. CCI
[REDACTED]
[REDACTED]

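### The primary responder rule gives no explicit status to patients whose permitted background DMARD, antimalarial or thalidomide is increased, or who start an antimalarial or thalidomide, before Week 29, and it is ambiguous for a newly started permitted DMARD

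*SAP*

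**What the plan says.** **Stability requirement.** Protocol Table 6-2 (Section 6.2.1) allows methotrexate, an imidazole derivative such as azathioprine or mizoribine, or a mycophenolic acid derivative if the dose has been stable "prior to randomization and remaining stable throughout blinded treatment period". It sets a similar condition for antimalarials and thalidomide, and allows one antimalarial to replace another at an equivalent dose. Protocol Section 3 adds that patients who enter without background corticosteroid (CS) "should remain free of any CS regimen or increase in SoC DMARDs through to Week 29". None of these statements carries a consequence for responder status.

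**Responder rule, protocol.** Section 12.4.1 lists the SRI-4 components and the CS conditions and then says: "When all these criteria are met, the patient is a responder". Its one further exclusion, for rescue medication, points to Section 6.2.4, which deals with CS only.

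**Responder rule, SAP.** Section 7.1.1 repeats the SRI-4 and CS conditions and adds as non-responders patients who drop out before Week 29 and "Patients who have taken other rescue medication or prohibited medication (Table 6-3 of study protocol, e.g., new immune suppressive agents or biologics".

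**Prohibited list.** The relevant row of protocol Table 6-3 is headed "Other immune suppressive agents and biologics". It names calcineurin inhibitors, cyclophosphamide, intravenous Ig, plasmapheresis and several biologics. The action for that row is "Withdrawal may be required on a case-by-case basis". Table 6-3 itself attaches non-responder status only to its two CS rows.

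**The concern.** The trial asks whether each antibody works when added to stable standard of care. If background therapy is stepped up during the blinded period, improvement at Week 29 may come from the background drug.

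The endpoint is sensitive to this because a sustained CS reduction is one of its required parts, and protocol 4.1.1 says DMARDs "are typically added as steroid-sparing agents to allow reduction of daily CS dosage". The guided taper from Week 5 to Week 17 is a time when an investigator might want to escalate. Consider a patient who worsens during the taper, has an existing DMARD increased, reaches the CS goal at Week 17 and loses 4 SLEDAI-2K points by Week 29. That patient meets every listed criterion. If the change is instead coded as a deviation that removes the patient from the PD set, the patient leaves the denominator and is still not counted as a failure. Dropouts and users of prohibited drugs, by contrast, are counted as failures.

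**Working it through.** **1. Each kind of change against each rule (public text)**

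| Change before Week 29 | Protocol 12.4.1 and 6.2.4 | Table 6-3 | SAP 7.1.1 | Status |
|---|---|---|---|---|
| CS increase beyond the allowance | covered | partly | covered | non-responder |
| Calcineurin inhibitor, cyclophosphamide, biologic | not covered | listed | covered | non-responder under the SAP |
| New methotrexate, azathioprine/mizoribine or mycophenolate | not covered | not listed | only if read as a new immune suppressive agent or as further rescue | ambiguous |
| Dose increase of a permitted DMARD | not covered | not listed | not a new agent; perhaps further rescue | not explicit |
| New or increased antimalarial or thalidomide | not covered | not listed | perhaps further rescue | not explicit |

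Neither document defines the SAP's category of other rescue medication.

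**2. What one patient does to a rate (30 per arm, protocol 12.8.1)**

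1/30 = 3.3 points; 2/30 = 6.7 points. Take a placebo arm with five responders plus one escalator who meets the SRI-4 and CS criteria:
- escalator counted as non-responder: 5/30 = 16.7%
- escalator counted as responder: 6/30 = 20.0%
- escalator excluded: 5/29 = 17.2%

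The second efficacy criterion needs a posterior probability above 50% that the difference exceeds 15 points. Under vague priors this needs about five more responders on active than on placebo, since 5/30 = 16.7% and 4/30 = 13.3%. At that boundary one reclassified patient changes the decision.

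**3. The plan's own figure**

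Inputs from protocol 12.4.2 and 12.8.1: 30 per arm, placebo 17%, active 17% + 25% = 42%, and both criteria, P(diff > 0) > 0.90 and P(diff > 0.15) > 0.50. The plan states an 84% chance of success, and about 10% if there is no difference.

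Method: for every pair of responder counts, decide whether both criteria hold under independent beta posteriors, then sum Binomial(30, p_active) × Binomial(30, p_placebo) over the pairs that pass. With Beta(0.5, 0.5) priors and no covariates this gives 81.2% and 6.0%; Beta(1, 1) gives the same to within 0.2 points. The first criterion alone gives 82.1% and 10.8%. The public text does not give the prior, so 84% is not called wrong. The comparisons below start from 81.2%.

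**4. Assumed scenarios**

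The documents give no escalation rate. The first column is the assumed number of points added to each arm when escalators count as responders. The base case counts every escalator as a non-responder.

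| Points added | Rates, active / placebo | Chance of meeting both criteria | Same, if both base rates are 17% |
|---|---|---|---|
| none (base) | 42 / 17 | 81.2% | 6.0% |
| +5 placebo only | 42 / 22 | 66.7% | 2.4% |
| +10 placebo, +5 active | 47 / 27 | 66.1% | 3.5% |
| +5 both arms | 47 / 22 | 80.2% | 8.0% |
| +5 active only | 47 / 17 | 90.5% | 16.2% |

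The size also depends on how many escalators go on to meet all criteria. Suppose 15% of placebo and 4% of active patients escalate. If half of them respond, the rates become 24.5% and 44%, and the chance is about 64%. If 17% of them respond, placebo becomes 17 + 0.17 × 15 = 19.6%, active 42 + 0.17 × 4 = 42.7%, and the chance is about 76%.

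**The case against.** The strongest reply is that the SAP already catches many of these patients. Some DMARD starts are covered: calcineurin inhibitors are in Table 6-3, and exclusion criterion 2 treats them as DMARDs ("calcineurin inhibitors, or other oral DMARD except as listed in inclusion criterion 6"). A newly started methotrexate or mycophenolate can reasonably be read as a new immune suppressive agent. Because the SAP mentions other rescue medication after setting out the CS rules, it may mean non-steroid treatment given for worsening disease, which could include a DMARD increase. A reader might infer that starting or increasing a DMARD never makes a patient a non-responder; the documents do not support that. What remains is that the SAP category is undefined, protocol 12.4.1 does not contain it, and protocol 6.2.4 describes rescue as CS only.

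Second, escalation breaches Table 6-2, so the patient might be removed from the PD set. The contents of SAP Table 4-1 are not shown, so this cannot be settled. Removal would not solve the problem, because it excludes a patient for an event after randomisation.

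Third, inclusion criterion 6, part of Table 6-2, protocol 8.3.2, SAP 7.1.3.1 and the SAP appendix are redacted or show no content, and derivation details sit in a separate programming specification. The finding is therefore limited to the visible text.

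Fourth, the study is non-confirmatory and the criteria are a guide for decisions. That lowers the stakes, but these criteria are still the stated basis for judging each drug.

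**Conclusion.** The gap stands for dose increases of permitted background DMARDs, antimalarials or thalidomide, and for newly started antimalarials or thalidomide: no visible passage explicitly makes these patients non-responders. For newly started methotrexate, azathioprine/mizoribine or mycophenolate the rule is ambiguous. An escalator who meets the SRI-4 and CS criteria can be counted as a responder or may be dropped from the PD set.

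A reader might infer that failing placebo patients escalate most, so that the gap mainly dilutes the treatment effect. That is plausible, but the documents establish neither the direction nor the size. More escalation on placebo would hide an effect; more on active would inflate it, with the false-positive chance rising from 6.0% to 16.2% in the assumed case of five extra points on active only. The range of 66% to 91% rests on assumed escalation rates, vague priors and no covariates. It shows that the decision is sensitive to the rule and does not forecast harm. The firm figure is 3.3 points per patient at 30 per arm.

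**What to change.** Reconcile protocol Section 3, Table 6-2, Table 6-3, 6.2.4 and 12.4.1 with SAP 7.1.1, and define what the SAP means by other rescue medication and by new immune suppressive agents. Then add one derivation rule to protocol 12.4.1 and SAP 7.1.1:

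- A patient who, between Day 1 and the Week 29 assessment, starts a DMARD, antimalarial or thalidomide, or takes more than the baseline dose of one, is a non-responder whatever the CS use, and stays in the primary analysis.
- The equivalent-dose antimalarial substitution allowed by Table 6-2 is exempt.
- Changes made for reasons other than SLE activity are reviewed case by case, as already provided for CS.

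This is an analysis rule only and changes no clinical management. Protocol 6.2.4 already requires all concomitant medications and dose changes in the eCRF, so no new data are needed. The cost is endpoint wording in both documents, one derivation, and possibly slightly lower observed responder rates.
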